In addition to the iLet itself, the entire iLet BP system includes a glass insulin cartridge, a glass glucagon cartridge, pigtail adapters that connect the drug cartridges to infusion sets, and a self-monitored blood-glucose (SMBG) meter. The SMBG meter that we will use is the Contour Next One (Ascensia). This meter is the successor to the Contour Next SMBG meter (Bayer), which was found to be the most accurate meter assessed in all three blood-glucose ranges tested (< 70, from 70 to 179, and ≥ 180 mg/dl) in a comparative accuracy study involving 17 point-of-care glucose meters.

I. e. Rationale and Potential Benefits

It has generally been assumed that the PK characteristics of rapid-acting insulin analogs are equivalent. This has led to them being treated as a commodity by insurance companies, who generally have only one rapid-acting analog on formulary. However, it is clear from our data that in many individuals there are differences between the PK of insulin lispro and insulin aspart that are consistent across 3 different experiments on different days. If these differences in PK affect glycemic regulation, then better glycemic control may be achieved by identifying a preferred insulin analog for an individual. To determine this, we will test lispro and aspart in the context of the bionic pancreas. We will further examine the effect of PK differences on glycemic control using the experimental ultra-rapid BC222 insulin lispro in a third bionic pancreas study arm, without altering the default PK parameters. An uncontrolled Test Run period with 4 subjects using the iLet with BC222 lispro for three days will be completed prior to initiating outpatient use of BC222 lispro in the iLet to verify safety and feasibility. Data from this Test Run will be reviewed before the RCT period can begin.

II. Hypothesis and Specific Aims

We hypothesize that differences in the PK characteristics of rapid and ultra-rapid insulin analogs will lead to differences in glycemic outcomes when delivered by the *insulin-only* configuration of the bionic pancreas. Specifically, we predict that insulin analogs that have faster absorption (numerically lower T_{max} and/or $T_{1/2max}$) and insulin analogs that have faster clearance (numerically lower terminal half-life) will result in lower mean glucose and/or a lower percentage of time in the hypoglycemic range.

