- There are no restrictions of any kind on diet or exercise in all three arms in the RCT portion of the study and the Test Run period, although subjects should attempt to maintain similar dietary habits and exercise habits during each arm of the study. The bionic pancreas must be kept dry during exercise.
- Subjects may choose to withdraw from the study at any time. If they withdraw from the study, they should contact a provider immediately who will help them transition to their own insulin regimen safely.

Test Run Policies Only

- Subjects in the Test Run period will be under supervision of study staff during the day. Subjects will be allowed to leave the clinic but will be restricted to the area immediately surrounding the clinic (e.g. within walking distance) and must be in contact with study staff regarding their location.
- While in the clinic, there will be no restrictions on physical activity and subjects will be encouraged to remain as physically active as they are in their normal life.
- Subjects will be required to check a BG at 1 and 2 hours after each meal announcement on all three days of the Test Run, including meal challenges and any other meal announcements delivered.
- Subjects will complete the meal challenges on days 2 and 3 of the Test Run period, following the same protocol as the RCT portion of the study.
- Subjects will be discharged from the clinic at the end of each day to home with a designated contact. During the first two nights at home, subjects will be instructed to check an overnight BG.

V. d. iv. Remote Monitoring

Local Alarms

- All alarm settings will be the same for the Test Run, the RCT portion of the study and during meal challenges.
- Alarms will sound and a visual alert will appear on the screen of the G5 mobile app when the CGM glucose is ≤ 70 mg/dl and the BP will alarm when the CGM glucose is ≤ 50 mg/dl.
 - Participants will be trained to test their BG with the study glucometer in response to such an alarm and take any necessary measures to treat hypoglycemia.

- Participants will be trained on troubleshooting for various scenarios that could lead to low threshold alarms. For instance, a threshold alarm could be due to true hypoglycemia, inaccurate CGM readings, or a compression artifact at the site of the sensor.
 - The first step for all glucose-related alarms will be to perform a fingerstick BG measurement.

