- Usage of CGM (type of CGM, days per month worn, usage of data, whether insulin is dosed based on CGM alone, alarm settings)
- Height and weight
- Blood pressure
- EKG if applicable
- Hemoglobin A1c
- Anti-insulin antibody titers
- Plasma, for future insulin antibody assays
- Urine HCG (pre-menopausal females)
- eGFR

VI. a. 2. All Study Arms (including the Test Run period):

- CGMG (CGM glucose) every five minutes from the Dexcom CGM
- All fingerstick BG measurements taken by the subject (meter download)
- Insulin total daily dose from bionic pancreas download
- Timing of meal announcements and size of meals announced from bionic pancreas download

- Day, time, fingerstick BG measurements, CGMG readings, and insulin doses from each meal challenge
- Time subjects were not under bionic pancreas control
- List of technical faults associated with the bionic pancreas including cause and resolution
- Body weight after each study arm
- Anti-insulin antibody titers and plasma after each study arm
- Date of last menstrual period
- Information collected from the daily email survey and phone calls including but not limited to hypoglycemia, carbohydrate interventions, any nausea and/or vomiting, any other adverse events, time spent exercising each day, exercise intensity, and exercise exposure (time X intensity), any unscheduled infusion set changes or Dexcom CGM sensor changes, and alcohol intake.
- Data from questionnaires about attitudes and expectations regarding the bionic pancreas at baseline and on day 7 of each arm (RCT portion the study only).

VI. b. Study Endpoints

Statistical comparisons will be made between insulin analogs within a single participant. Three pairwise comparisons will be made between arms.

Data from the uncontrolled Test Run period will be reviewed to verify safety before proceeding with the RCT portion of the study. Descriptive statistics will be compiled based on the same analyses planned for the RCT portion of the study but no formal statistical analyses will be done. This period has no control and is intended to verify the iLet with BC222 lispro is safe and operating as expected prior to initiating outpatient experiments in a larger cohort.

VI. b. 1. Co-Primary endpoint analyses

The co-primary outcomes will be mean CGMG and fraction of time spent with CGMG <54 mg/dl.

VI. b. 2. Secondary endpoint analyses

Secondary analyses will include:

- Fraction of time spent within each of the following ranges:
 - < 50 mg/dl
 - < 60 mg/dl

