we believe that the risk of hypoglycemia will be less than or equal to the risks that they are exposed to on a daily basis while living with type 1 diabetes outside of the trial.

Even though no increase in hypoglycemia was observed in subjects with T1D using BC222 inuslin lispro under MDI or open-loop regimen, there may be an increased risk of hypoglycemia with the ultra-rapid BC222 insulin lispro, which is expected to have a faster onset than rapid acting analogs. Subjects will be trained on the recognition and treatment of hypoglycemia, and the risk of using an ultra-rapid insulin will be explained to them. We anticipate the bionic pancreas will adapt to the faster pharmacokinetic profile of BC222 insulin lispro, and that hypoglycemia will not be higher than what the insulin-only bionic pancreas is able to achieve with rapid-acting insulin. We believe that the risk of hypoglycemia is further mitigated by keeping the PK parameter settings of the iLet at 65 minutes, despite the possibility BC222 is faster than that. The Test Run period using BC222 lispro in the iLet in a supervised setting will be completed and reviewed for safety prior to initiating any outpatient experiments using BC222 lispro.

There is a risk of hyperglycemia. This risk is expected to be similar to or less than the risk during the subjects' lives outside of the trial based on data from earlier trials in subjects with type 1 diabetes.

VIII. Potential Benefits

Based on evidence from previous trials of the bionic pancreas and the design of this trial, subjects enrolled in the study may benefit from a reduction in risk of hypoglycemia and hyperglycemia and a better mean glucose than they typically achieve.

Subjects are expected to benefit in all arms of the study from the formal involvement of a designated contact who will serve as a backup to respond to any overnight threshold alarms to which the subject does not respond.

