A numeric code will be substituted for the subject's personal identifying information in the study database, which will be password protected. The key linking the medical record number of the subject with the numeric code, along with case report forms, and all information that is personally identifiable, will be kept in a locked filing cabinet in an investigator's locked office. All electronic records will be kept in a password protected computer database. All printed computer data will be disposed of confidentially when no longer needed. Only the study staff will have access to the study database. Subjects may not withdraw from the de-identified database, but they may elect to have the key linking their medical record to the de-identified database destroyed.

The study data may be shared with collaborators at Beta Bionics and Adocia but only in a form in which all personally identifiable information has been removed (e.g. combined database including BG values, CGM values, and record of insulin delivered by the device). Shared data will be in the form of a database in which only a number identifies subjects.

Subjects may not withdraw their data, as it will be stored in non-personally identifiable form.

IX. b. Safety Monitoring

This study is considered moderate risk. An external Data and Safety Monitoring Board will oversee the conduct of the study and review its results on a regular basis. The DSMB will be responsible for overseeing the transition from the Test Run period to the RCT portion of the study. They will be informed of any events described in the stopping criteria below that occur in the Test Run period. If there are no events for DSMB review, then the RCT portion of the study will be initiated prior to their review of the data.

Additionally, the DSMB will be informed in the event of any severe or unexpected adverse events in the RCT portion of the study. The DSMB will have unblinded access to the drug assignments to assess whether adverse events are associated with insulin administration. The DSMB will be informed if there are any changes to the study protocol that could significantly impact the safety or scientific validity of the study. A final DSMB meeting will convene after the completion of the study. Safety and efficacy data will also be reported to the FDA in compliance with applicable regulations.

The participation of individual subjects will be discontinued if they experience:

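### If the Test Run produces no stopping-criteria event, the RCT opens before the DSMB has reviewed any Test Run data, although the DSMB is charged with overseeing that step

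*Combined protocol and SAP*

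**What the plan says.** The first paragraph of section IX.b (Safety Monitoring) sets out the board's part in three steps:

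- Its role: "The DSMB will be responsible for overseeing the transition from the Test Run period to the RCT portion of the study".
- What it is told: "They will be informed of any events described in the stopping criteria below that occur in the Test Run period".
- What happens if no event calls for its attention: "then the RCT portion of the study will be initiated prior to their review of the data".

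Three other sections promise a review before the RCT:

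- I.e (Rationale): "Data from this Test Run will be reviewed before the RCT period can begin".
- VI.b (Study Endpoints): "Data from the uncontrolled Test Run period will be reviewed to verify safety before proceeding with the RCT portion of the study".
- VII (Risks and Discomforts): the Test Run "will be completed and reviewed for safety prior to initiating any outpatient experiments using BC222 lispro".

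None of the three says who reviews or what result would allow the RCT to open. VI.b plans descriptive statistics for the Test Run on the same outcomes as the RCT, with no formal analysis. VI.c calls the four participants a convenience sample.

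Section V.b states that BC222 lispro had not been used in a bionic pancreas before. Section VII accepts that its faster onset may raise the risk of hypoglycemia and offers the Test Run as one of the mitigations.

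**The concern.** The Test Run exists to show that a new drug-device pairing is safe enough for a larger group to use at home. The board that oversees the decision to go on will, if nothing triggers notification, have seen none of the evidence when the RCT opens.

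The trigger is also coarse. Its clinical items are hospitalised DKA and severe hypoglycemia, whereas the most informative product of three days in four people is the continuous glucose record. If BC222 lispro caused more time at low glucose without a severe episode, that signal would sit in data the board need not see before the RCT. At stake is independent oversight of up to 30 participants' first week on this pairing.

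**Working it through.** **1. The relevant text side by side**

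| Question | IX.b | I.e, VI.b and VII |
|---|---|---|
| Who is responsible for the transition? | DSMB | Not stated |
| Who reviews the data before the RCT? | Not the DSMB, if there is no event | Not stated |
| Against what criteria? | Occurrence of a stopping-criteria event | Not stated |

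A study-team review before the RCT would satisfy I.e, VI.b and VII, and DSMB review afterwards would satisfy IX.b. The four sections can therefore all be true together. The tension lies inside IX.b: responsibility for the transition, without sight of the data when it happens.

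**2. What can reach the DSMB before the RCT**

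Read at its widest, the list in IX.b covers DKA requiring hospitalisation, severe hypoglycemia, an investigator's judgement that continuing is unsafe, pregnancy, and a participant's request to stop. No item is defined by glucose values. Section IX.c records a hypoglycemic event as an adverse event only if it is severe. Non-severe hypoglycemia is thus neither a listed criterion nor a recorded adverse event, and it is unlikely to enter the 72-hour reporting of serious and unexpected events. Time below 54 mg/dl is a co-primary outcome (VI.b.1), but nothing requires the board to see it before the RCT.

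**3. How much does a silent trigger tell us?**

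The plan gives no operating characteristics for this gate, so there is no figure to reproduce. What follows is an illustration.

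Inputs: n = 4 participants over 3 days (I.e). The per-person risk p of a triggering event over those 3 days is my assumption, because the documents give none. Participants are treated as independent with equal risk.

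P(no event in 4) = (1 − p)^4

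| Assumed p | Calculation | P(no event): RCT opens before DSMB data review | P(at least one event): DSMB informed first |
|---|---|---|---|
| 1% | 0.99^4 = 0.961 | 96% | 4% |
| 5% | 0.95^4 = 0.815 | 81% | 19% |
| 10% | 0.90^4 = 0.656 | 66% | 34% |
| 20% | 0.80^4 = 0.410 | 41% | 59% |

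**4. Exposure on each side of the gate**

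Test Run: 4 × 3 = 12 person-days on BC222 lispro. RCT: up to 30 × 7 = 210 person-days on BC222 lispro.

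**The case against.** The strongest reply is that IX.b describes oversight by exception and says so openly: the board is responsible, hears of triggering events, and otherwise lets the RCT proceed with data review to follow. That is a coherent arrangement. Preferring a review first is a judgement about how a DSMB should work, not the correction of an error. This stands, and it is why the point is a recommended improvement rather than a defect that invalidates the plan.

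A reader might infer that the only check on the pairing can be bypassed. The documents do not support that. Besides notification of triggering events, the plan has:

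- remote alarms when CGM glucose is below 50 mg/dl for 15 minutes (V.d.iv);
- reporting of serious and unexpected events to the DSMB within 72 hours (IX.b);
- a study halt, with a DSMB vote to restart, if more than one participant is withdrawn for the listed severe events (IX.b);
- investigator review of adverse events after each experiment (IX.c).

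These protect individuals or act once an event has occurred. None gives the board the Test Run glucose data beforehand.

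A reader might also infer that I.e, VI.b and VII contradict IX.b. They do not, because they name no reviewer. Nor is the trigger confined to DKA and severe hypoglycemia: an investigator worried by CGM lows could discontinue a participant, and that could reach the board.

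On size, the risks in the table are assumptions. The plan's own evidence is reassuring: more than 280 people exposed for up to 14 days with no identified risk beyond those of insulin products (V.b), and no increase in hypoglycemia under injections or open-loop use (VII). None of that exposure was with a bionic pancreas. It is also tempting to cite the exact one-sided 95% upper bound after 0 of 4 events, 1 − 0.05^(1/4) = 53%. That bound reflects the sample of four and would be the same whoever reviewed the data, so it does not support this point.

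**Conclusion.** The point holds in a limited form. If no stopping-criteria event occurs, the RCT opens before the DSMB reviews Test Run data, although IX.b makes the board responsible for that transition. The criteria have no glucose-based item, so excess non-severe hypoglycemia need not reach the board first. The plan does not say who carries out the review promised elsewhere, or against what.

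A trigger that would stay silent 81% of the time at an assumed 5% risk, and 41% of the time even at 20%, is weak reassurance when it is silent. These figures rest on assumed, equal and independent risks and show only how little four people can reveal through rare events. They do not suggest that BC222 lispro carries such risks. The conclusion about oversight rests on the text and does not depend on them.

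Separately, and less importantly, I.e places the Test Run ahead of outpatient use and VII calls its setting supervised, while the Test Run policies in V.d.iii state: "Subjects will be discharged from the clinic at the end of each day to home with a designated contact". The night-time arrangements are disclosed, with remote monitoring and an overnight glucose check on the first two nights, so this is loose wording that needs reconciling.

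**What to change.** Replace the last sentence of the first paragraph of IX.b with text to this effect: *The RCT will not open until the DSMB has received the Test Run summary (adverse events, and mean CGMG and time below 54 and below 70 mg/dl for each participant) and has confirmed that the RCT may proceed.* The glucose outcomes belong to the descriptive analysis already planned in VI.b, so the summary amounts to a short listing of four people.

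Make I.e, VI.b and VII agree with IX.b on who reviews. Naming the DSMB there is a design choice that follows from the new sentence, since those sections currently name nobody. If the sponsor prefers to keep oversight by exception, the protocol should at least state who reviews which Test Run data before the RCT, and on what basis it may open.

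Separately, reconcile the supervised-setting and before-outpatient-use wording in I.e and VII with the nightly discharge home in V.d.iii and V.d.v.

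Cost: a short protocol amendment, and a brief delay between the Test Run and the RCT for one DSMB call or e-mail review. No extra participants, visits or procedures are needed.

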- Subjects experience one episode of diabetic ketoacidosis (DKA) requiring hospitalization
 - Hyperglycemic events will be classified as DKA if the following are present:
 - Symptoms including but not limited to polyuria, polydipsia, nausea or vomiting
 - Serum ketones $> 1.5 \text{ mmol/L}$ or large/moderate urine ketones
 - Either arterial blood pH < 7.30 or venous pH < 7.24 , or serum bicarbonate < 15
 - Treatment provided in a healthcare facility
- Subjects experience one episode of severe hypoglycemia, defined as requiring the assistance of another person due to altered consciousness, and required another person to actively administer carbohydrate, glucagon or other resuscitative actions. This means the participant was impaired cognitively to the point that he/she was unable to treat himself/herself, was unable to verbalize his/her needs, was incoherent, disoriented, and/or combative, or experienced seizure or coma. If plasma glucose measurements are not available during such an event, neurological recovery attributable to the restoration of plasma glucose to normal is sufficient evidence that the event was induced by a low plasma glucose concentration.
- The investigator believes it is unsafe for the participant to continue in the study
- A participant becomes pregnant

- The participant requests that the study be stopped

If more than 1 subject must be withdrawn from the study for DKA requiring hospitalization or seizure or unconsciousness associated with hypoglycemia the study will stop and a vote of the DSMB will be required to restart it. All serious and unexpected events will be reported to the DSMB within 72 hours.

Note that subjects may discontinue participation at any time and subjects may be removed from the trial for other reasons, for instance failure to comply with study procedures or concurrent illness that is unrelated to the bionic pancreas but that precludes safe participation. Discontinuation of participation for these reasons will not contribute to a decision to discontinue the trial.

IX. c. Adverse Event Definitions and Reporting Guidelines

Definitions

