To ensure consistency of adverse event causality assessments, investigators should apply the following general guideline when determining whether an adverse event is related:

Related: There is a plausible temporal relationship between the onset of the adverse event and the study intervention, and the adverse event cannot be readily explained by the participant's clinical state, intercurrent illness, or concomitant therapies; and/or the adverse event follows a known pattern of response to the study

intervention; and/or the adverse event abates or resolves upon discontinuation of the study intervention or dose reduction and, if applicable, reappears upon re-challenge.

Possibly Related: Possibly related to the research means there is a reasonable possibility that the adverse event, incident, experience or outcome may have been caused by the procedures involved in the research (modified from the definition of associated with use of the drug in FDA regulations at 21 CFR 312.32(a)). Reasonable possibility means that the event is more likely than not related to participation in the research or, in other words, there is a >50% likelihood that the event is related to the research procedures

Not Related: Evidence exists that the adverse event has an etiology other than the study intervention (e.g., preexisting medical condition, underlying disease, intercurrent illness, or concomitant medication); and/or the adverse event has no plausible temporal relationship to study intervention.

Serious adverse event means any event temporally associated with the subject's participation in research that meets any of the following criteria:

- results in death
- is life threatening (places the subject at immediate risk of death from the event as it occurred)
- requires inpatient hospitalization or prolongation of existing hospitalization; • results in a persistent or significant disability/incapacity
- results in a congenital anomaly/birth defect
- any other adverse event that, based upon appropriate medical judgment, may jeopardize the subject's health and may require medical or surgical intervention to prevent one of the outcomes listed above (examples of such events include allergic bronchospasm requiring intensive treatment in the emergency room or at home, blood dyscrasias or convulsions that do not result in inpatient hospitalization, or the development of drug dependency or drug abuse).

Reporting Guidelines

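### Withdrawals for severe hypoglycemia without seizure or unconsciousness never count toward the study stop, and no deadline for telling the DSMB is assured

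*Combined protocol and SAP*

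**What the plan says.** Section IX.b (Safety Monitoring) works at two levels.

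- **Individual withdrawal.** The list includes: "Subjects experience one episode of severe hypoglycemia, defined as requiring the assistance of another person due to altered consciousness". The definition goes on to require active rescue by another person. It covers a participant who is incoherent, disoriented or combative, as well as one with seizure or coma. The list also includes one episode of DKA requiring hospitalization.
- **Study stop.** "If more than 1 subject must be withdrawn from the study for DKA requiring hospitalization or seizure or unconsciousness associated with hypoglycemia", the study stops and only a DSMB vote can restart it.

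Reporting to the DSMB is set out in three places in IX.b:

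- In the RCT, "the DSMB will be informed in the event of any severe or unexpected adverse events in the RCT portion of the study". No time limit is attached.
- "All serious and unexpected events will be reported to the DSMB within 72 hours".
- After noting that participants may leave for other reasons, such as non-compliance or unrelated illness, the section adds: "Discontinuation of participation for these reasons will not contribute to a decision to discontinue the trial".

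Section V.d.vi (Response to Hypoglycemia) has a second, narrower individual rule, limited to seizure or unconsciousness with hypoglycemia. Section V.d.vii has the matching rule for hospitalized DKA.

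**The concern.** The two limbs of the study stop do not relate to the individual list in the same way. For DKA, the event that withdraws a participant and the event that counts toward the stop are identical. For hypoglycemia, the stop counts only part of what withdraws a participant. Its wording follows V.d.vi rather than the broader definition a few lines above it in IX.b.

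Two or more participants could thus be withdrawn because another person had to rescue them from a hypoglycemic episode with altered consciousness, and no pause or DSMB vote would be required. The DSMB could still act on its own initiative, but that depends on prompt notice, and the plan sets no deadline that surely covers these episodes.

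The setting makes this worth settling. Section V.b says that BC222 insulin lispro had not been tested in a bionic pancreas. Section VII allows that it may raise the risk of hypoglycemia, while noting that no increase was seen with injections or open-loop use. In a trial of up to 30 people, two assisted severe episodes would be a notable signal.

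**Working it through.** **Step 1: which events reach which rule (IX.b).**

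| Event leading to withdrawal | Counts toward stop? |
|---|---|
| DKA requiring hospitalization | Yes |
| Severe hypoglycemia with seizure or unconsciousness | Yes |
| Severe hypoglycemia, assisted, without either | No |

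**Step 2: does the 72-hour rule cover the third row?** The rule can be read in two ways.

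- *Serious and also unexpected, both required.* An episode classed as expected falls outside. Section VII lists hypoglycemia as a risk, and the plan does not say whether a severe episode is expected.
- *Serious events, and separately unexpected events.* An expected episode is covered only if judged serious. Without admission, that requires it to be life threatening or to meet the catch-all in IX.c: "any other adverse event that, based upon appropriate medical judgment, may jeopardize" the participant's health. The examples there include convulsions without admission, but not an assisted episode with disorientation.

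On neither reading is coverage assured. The 48-hour limit in IX.c runs to the principal investigator, not to the DSMB.

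**Step 3: illustrative size.** The plan gives no operating characteristic for the stop, so there is no figure to reproduce.

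Inputs: N = 30 (the RCT maximum in IV.a). Assumed: p, the chance that a participant is withdrawn for severe hypoglycemia during the RCT, 1% or 2%; q, the share of these with seizure or unconsciousness, 0.25 to 0.75; no DKA withdrawals; participants independent.

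For a per-participant risk x, the chance of two or more withdrawals is

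P(≥2; x) = 1 − (1 − x)^30 − 30x(1 − x)^29.

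The stop as written uses x = pq. A stop that counts all severe hypoglycemia uses x = p. With no DKA, a stop as written implies at least two severe-hypoglycemia withdrawals. So the chance of two or more withdrawals with no stop is the difference P(≥2; p) − P(≥2; pq). Differences below are taken before rounding.

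| p | q | All severe counted | As written | Two or more, no stop |
|---|---|---|---|---|
| 1% | 0.25 | 0.0361 | 0.0026 | 0.0336 |
| 1% | 0.50 | 0.0361 | 0.0099 | 0.0262 |
| 1% | 0.75 | 0.0361 | 0.0213 | 0.0149 |
| 2% | 0.25 | 0.1205 | 0.0099 | 0.1106 |
| 2% | 0.50 | 0.1205 | 0.0361 | 0.0844 |
| 2% | 0.75 | 0.1205 | 0.0742 | 0.0463 |

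**Step 4: are these values of p reasonable?** Three 7-day arms in 30 people give 30 × 21 = 630 person-days, or about 1.73 person-years. Then p = 1% means 0.3 / 1.73 = 0.17 events per person-year, and p = 2% means 0.6 / 1.73 = 0.35. Section III.b excludes anyone with severe hypoglycemia in the last 6 months or more than one episode in the last year. Together with the alarms and remote monitoring in V.d.iv, this favors the lower value.

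**The case against.** A narrower trigger at study level than at participant level is an ordinary design, and V.d.vi uses the same wording as the stop, which may mean that the tier was chosen. That stands: a reader might infer a contradiction, and the documents do not show one. They show a difference that is present for hypoglycemia, absent for DKA and unexplained.

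A reader might also infer that the DSMB would not hear of these episodes, or that they are barred from influencing a decision to stop. Neither follows. IX.c calls exactly these episodes severe hypoglycemic events, so the RCT notice in IX.b most naturally reaches them. The DSMB has unblinded access and regular oversight. The sentence on withdrawals that do not contribute to stopping concerns other reasons, not the listed ones. What is missing is a deadline and a required decision.

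It can be argued that the plan uses severe and serious loosely for one idea, since IX.c describes severity as serious or non-serious. The 72 hours would then be the deadline for the RCT notice. That reading is possible, but the 72-hour sentence still adds unexpected, so the ambiguity remains.

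Finally, a reader might extend the point to the Test Run, where the DSMB hears of "They will be informed of any events described in the stopping criteria below that occur in the Test Run period", and where "If there are no events for DSMB review, then the RCT portion of the study will be initiated prior to their review of the data". That extension is weak. The individual list follows directly and fits a phrase about events better than a rule about a count does. Section I.e also requires a review of Test Run data before the RCT begins.

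**Conclusion.** The point holds as a gap in the safety rules, not as an error or contradiction. As IX.b is written, repeated severe-hypoglycemia withdrawals without seizure or unconsciousness never require a DSMB vote, and no deadline is certain to govern when the DSMB hears of them.

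The gap is modest in probability. The chance of two or more severe-hypoglycemia withdrawals with no automatic stop is 1.5% to 3.4% at p = 1%, and 4.6% to 11.1% at p = 2%, over q from 0.25 to 0.75. Both p and q are assumptions with no basis in the documents, and N = 30 is the planned maximum. The textual finding does not depend on them. The change merits consideration because it is cheap and concerns the safety of participants using an insulin new to this device.

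**What to change.** In IX.b:

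1. Require that every withdrawal for severe hypoglycemia be reported to the DSMB within 72 hours, whatever its seriousness or expectedness.
2. In the stop sentence, replace the seizure-or-unconsciousness wording with severe hypoglycemia as defined in the individual list. If the narrower automatic stop is intended, say so, and require a DSMB decision on continuation after the second severe-hypoglycemia withdrawal.

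Cost of item 1: at most 30p expected extra reports over the RCT, which is 0.3 at p = 1% and 0.6 at p = 2%.

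Cost of item 2, first option: more frequent but reversible pauses. At q = 0.50 the chance of a pause rises from 1.0% to 3.6% at p = 1%, and from 3.6% to 12% at p = 2%. The second option avoids these added automatic pauses and still secures a DSMB decision.
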